6.5.15 Pharmacodynamic Biomarker Analyses

Pharmacodynamic biomarkers other than serum creatinine, serum and CSF NfL, and urinary p75[ECD] will be analyzed by Clene Nanomedicine according to a separate pharmacodynamic DAP (Regimen C Pharmacodynamic Analysis Plan) and will be reported in a separate report.

6.5.16 Pharmacokinetics of Riluzole

Pharmacokinetic analysis of plasma riluzole concentrations will be analyzed according to a separate pharmacokinetic analysis plan authored and conducted by [name], PharmD.

6.6 Safety Analyses

6.6.1 Treatment-emergent Adverse Events

Summaries and analyses of treatment-emergent adverse events (TEAE) are the same as specified in the M-SAP with the following revisions.

TEAEs are defined as those adverse events with onset dates in the interval from double-blind treatment initiation to either the Final Safety Visit if completed, the date of death if the participant dies, 28 days after last dose of study drug if the participant early terminates or is lost to follow-up, or the date of first dose of study drug during participation in the OLE, if so exposed. Adverse events with onset on the day of double-blind treatment initiation and adverse events with incompletely specified onset date where the ambiguous date spans the day of double-blind treatment initiation will be assumed to be treatment emergent except for those known to precede first exposure to study drug.

In addition to summaries specified in the M-SAP, serious TEAEs will be summarized by MedDRA system organ class, high level term, and preferred term for all TEAEs. In addition, TEAEs will be summarized by Medical Dictionary for Regulatory Activities (MedDRA) system organ class and preferred term for fatal TEAEs, TEAEs that occurred during a participant's COVID-19 infection (defined as 5 days prior to symptom onset to end of COVID-19 symptoms

or the earlier of 91 days after symptom onset or the end of double-blind follow-up, if ongoing), and TEAEs and serious TEAEs stratified by the following subgroups: baseline riluzole use, baseline edaravone use, age, sex, race, ethnicity, weight, BMI, and CKD stage. Subgroup classifications will be the same as described in Section 6.5.12 Subgroup Analyses except that the "other" group will be retained regardless of prevalence.

TEAEs indicating COVID-19 infection are the following: Asymptomatic COVID-19, COVID-19, COVID-19 pneumonia, COVID-19 treatment, Post-acute COVID-19 syndrome, SARS-CoV-2 antibody test positive, SARS-CoV-2 RNA increased, SARS-CoV-2 sepsis, SARS-CoV-2 test false negative, SARS-CoV-2 test positive, SARS-CoV-2 viraemia, Suspected COVID-19.

Treatment-dependent differences in the proportion of participants experiencing a given type of TEAE will not be tested. Treatment-dependent differences in TEAE incidence rates in units of number per 100 participant years will be estimated as differences rather than ratios and will include comparison-wise 95% confidence intervals with variance estimates obtained by the delta method.

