		Clinic	Clinic	Clinic	Phone	Clinic	Clinic	Phone	Clinic	Phone	Clinic	Phone
		-42 to -1 Days	-41 to 0 Day	Day 0	Day 14 ±3	Day 28 ±7	Day 56 ±7	Day 84 ±3	Day 112 ±7	Day 140 ±3	Day 168 ±7	28 days after last dose ±3 days
Biomarker Urine Collection	Master			X			X		X		X	
DNA Collection ⁷ (optional)	Master			X								
CSF Collection (optional)	Master			X					X ¹⁵			
Concomitant Medication Review	Master	X	X	X	X	X	X	X	X	X	X	
Adverse Event Review ⁶	Master	X	X	X	X	X	X	X	X	X	X	X
Columbia-Suicide Severity Rating Scale	Master			X		X	X		X		X	
Install Smartphone App ¹⁹	Regimen			X								
Voice Recording ⁹	Regimen			X		X	X		X		X	
Uninstall Smartphone App	Regimen										X	
Assignment to the Regimen	Master	X										
Randomization within the Regimen	Master		X									
Administer/Dispense Investigational product	Master			X ⁸			X		X		X ¹⁰	
Study Drug Accountability/Compliance	Master				X ²⁰	X	X	X ²⁰	X	X ²⁰	X	
Exit Questionnaire	Master										X	
Vital Status Determination ¹³	Master										X	

¹ Master Protocol Screening procedures must be completed within 42 days to 1 day prior to the Baseline Visit. The Regimen-Specific Screening Visit and Baseline Visit should be combined, if possible.

² During the Master Protocol Screening Visit, participants will be consented via the Master Protocol informed consent form (ICF). After a participant is randomized to a regimen, participants will be consented a second time via the regimen-specific ICF.

³ At the Regimen Specific Screening Visit, participants will have regimen-specific eligibility criteria assessed.

⁴ Vital signs include weight, systolic and diastolic pressure, respiratory rate, heart rate and temperature. Height measured at Master Protocol Screening Visit only.

⁵ Clinical safety labs include hematology (CBC with differential), complete chemistry panel, thyroid function and urinalysis. Serum pregnancy testing will occur in women of child-bearing potential at the Master Protocol Screening Visit and as necessary during the study. Pregnancy testing is only repeated as applicable if there is a concern for pregnancy.

⁶ Adverse events that occur after signing the consent form will be recorded.

⁷ The DNA sample can be collected after baseline if a baseline sample is not obtained or the sample is not usable.

⁸ Administer first dose of investigational product only after Baseline Visit procedures are completed.

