⁸ At all visits, whether conducted in-clinic or via telemedicine (or via phone if telemedicine is not available), vital signs include systolic and diastolic blood pressure, heart rate, respiratory rate, and temperature. At all in-clinic visits, vital signs include weight. At the MP Screening Visit only, vital signs include height measured in cm.

⁹ If required due to pandemic-related restrictions, forced vital capacity (FVC) performed by a Pulmonary Function Laboratory evaluator or with a study-approved home spirometer or sustained phonation using a study-approved method may be used for eligibility (Master Protocol Screening ONLY).

¹⁰ Clinical safety labs include hematology (CBC with differential), complete chemistry panel, liver function tests, thyroid function, and urinalysis. Serum pregnancy testing will occur in women of child-bearing potential at the Master Protocol Screening Visit and as necessary during participation. Pregnancy testing is only repeated as applicable if there is a concern for pregnancy.

¹¹ Whole blood samples for CNM-Au8 PK, plasma samples for riluzole PK, and whole blood, plasma, and urine samples for PD biomarkers should be obtained prior to the first daily dose of study drug at each applicable clinic visit. The time of the most recent dose of study drug, the most recent meal prior to sampling, and the time of sample collection should be reported. Whole blood and urine will be collected only at the Baseline and Week 24/Early Termination visits.

¹² If the participant consents to DNA sample collection but a DNA sample is not obtained at the Baseline Visit or if that sample is not usable, a DNA sample can be collected after the Baseline Visit.

¹³ If the participant consents to CSF sample collection but a CSF sample is not obtained at the Week 16 Visit, a CSF sample can be collected at the Week 24 Visit.

¹⁴ Adverse events that occur after signing the RGC ICF will be recorded.

¹⁵ Two smartphone apps should be installed on the participant's phone, one to collect home spirometry and one to collect voice recordings.

¹⁶ In addition to study visits specified in the SoA for collection of voice recordings, participants should complete twice weekly voice recordings at home. During weeks when a participant completes a voice recording in-clinic, he or she should only complete one other voice recording at home.

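### SAP 6.6.1 defines treatment-emergent events by onset date alone, so a pre-dose adverse event that worsens on study drug and keeps its original onset date is omitted from the TEAE tables

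*SAP*

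**What the plan says.** SAP 6.6.1 opens by deferring to the master plan: "Summaries and analyses of treatment-emergent adverse events (TEAE) are the same as specified in the M-SAP with the following revisions". The first revision is the definition itself: "TEAEs are defined as those adverse events with onset dates in the interval from double-blind treatment initiation". The window closes at the final safety visit, death, 28 days after the last dose (for early termination or loss to follow-up) or the first open-label dose, as applicable. Events that start on the day of first dosing, or whose incomplete onset date spans that day, "will be assumed to be treatment emergent except for those known to precede first exposure to study drug".

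The outputs follow from that definition. For serious events, "serious TEAEs will be summarized by MedDRA system organ class, high level term, and preferred term for all TEAEs". Fatal, COVID-19-period and subgroup tables are also tables of TEAEs. For the comparison between groups, "Treatment-dependent differences in TEAE incidence rates in units of number per 100 participant years will be estimated as differences rather than ratios".

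The documents differ on when recording starts. Footnote 6 of the protocol's placebo-controlled Schedule of Activities says "Adverse events that occur after signing the consent form will be recorded", without saying which of the two consent forms is meant. Footnote 14 of SAP 2.9 says "Adverse events that occur after signing the RGC ICF will be recorded". Both schedules mark adverse event review at Master Protocol Screening, regimen screening and Baseline.

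**The concern.** A TEAE definition usually has two parts: events that begin on treatment, and events that were already present and get worse on treatment. Section 6.6.1 contains only the first. Adverse events are collected before first dose, so records with a pre-dose onset can exist, and the plan has no rule that brings one into the TEAE count if it later deteriorates.

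Treatment-emergent adverse and serious adverse events are the first safety endpoint listed in Protocol 2.1, so the definition governs a main safety output. An effect of the drug on an event already under way would appear as worsening rather than as a new onset. Protocol 5.5 (Dosage Adjustment) names gastrointestinal disturbance, headache and somnolence as possible tolerability issues. Complaints of that kind could begin during screening and change after dosing. Protocol 5.10.1.1 also notes that human exposure is limited, so even one uncounted serious or fatal worsening would matter.

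**Working it through.** The plan gives no figure on this point, so the check is a reading of the rules together.

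**1. Is there a worsening provision elsewhere in the SAP?** No. Section 6.6.1 tests onset date only. Severity, seriousness and outcome do not enter the definition.

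**2. Could the master SAP supply one?** It was not available. However, 6.6.1 presents its definition as a revision, and SAP section 1 makes the regimen SAP prevail over the master SAP on analysis matters of this kind. A worsening provision in the master SAP would be superseded, or at best be in dispute.

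**3. Can pre-dose records exist?** Yes. First dose follows all Baseline procedures.
- Master Protocol Screening runs from day -42 to day -1. If recording starts there, the pre-dose period is 1 to 42 days.
- Regimen screening runs from day -41 to day 0. If recording starts at regimen consent, as in SAP footnote 14, the period is 0 to 41 days. It is about zero when regimen screening and Baseline are combined, which Protocol 6.1 asks for where possible.

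**4. What happens to an event that starts in that period and worsens after dosing?**
- If the existing record is updated, onset stays pre-dose. The event is not a TEAE, and so not a serious or fatal TEAE, and it does not enter the rates.
- If the worsening is entered as a new record dated at the worsening, its onset falls in the window and 6.6.1 counts it.
- If the original onset date is incomplete and spans the first-dose day, the event counts unless it is known to precede first exposure.

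SAP section 1 refers definitions and reporting of adverse events to the Master Protocol (not supplied) and the regimen appendix. The regimen appendix does not say which of the first two routes applies.

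**5. What else would show such an event?**
- SAP 6.6.2: laboratory shift tables, including maximum post-baseline grade. These cover laboratory values, not symptoms.
- SAP 6.5.4: survival in the safety sets, with listings. This covers deaths, without an event term.
- SAP 5.12 and 6.5.6: time to first hospitalization for an SAE. It is a composite with death or death equivalent, is analyzed in the efficacy sets, and misses worsening without hospitalization.
- SAP 6.7.2: study drug interruptions and dosage reductions, without an event term.

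**6. Size.** With N active participants, the number omitted is N × r × o × w × k. Here r is pre-dose events per participant, o the fraction ongoing at first dose, w the fraction of those that worsen, and k the fraction kept under the original onset date. Only N = 120 is in the documents. As an illustration on assumed values:
- r = 0.2, o = 0.5, w = 0.05, k = 1: 120 × 0.2 × 0.5 × 0.05 = 0.6.
- r = 0.5, o = 0.5, w = 0.10, k = 1: 120 × 0.5 × 0.5 × 0.10 = 3.0.
- r = 0 (same-day consent and dosing) or k = 0 (worsening always a new record): 0.

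This shows what the count depends on. It is not an estimate.

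**The case against.** The strongest reply is that the omission depends on a recording convention nobody can see here. If the Master Protocol requires a worsening to be a new adverse event with its own date, 6.6.1 already counts it and no event is lost. That stands, and it is why the point is conditional. It does not make the section adequate: 6.6.1 neither states nor cites such a convention, so a reader of the supplied plan cannot tell how a worsening is counted.

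A second reply is that the affected group is narrow: adverse events that begin after consent and are still present at first dose. Complaints that predate consent belong to medical history, and nothing supplied gives them an adverse event onset date. This also stands, and under the SAP's start of recording the window may often be close to zero days.

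Third, the point affects no efficacy inference, and SAP 6.6.1 does not test differences in TEAE proportions. True, but the rate differences with confidence intervals use the same definition.

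A reader might infer that every on-treatment worsening disappears from the report, or that a drug aggravating existing complaints would show no signal. The documents do not support that: the outputs in step 5 would show part of it, and a worsening entered as a new record would be in the TEAE tables. A reader might also compare the longest screening window with the treatment period (42/168 = 25%) and take that as the share of events at risk. It is a ratio of maximum durations, not of events. Adding 28 days of follow-up for those not entering the extension lowers it to 42/196 = 21%, and neither figure says how many events persist or worsen.

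**Conclusion.** The point holds in conditional form. The definition rests on onset date alone, and the regimen SAP's precedence means the master SAP cannot be relied on to widen it. A pre-dose adverse event that worsens, becomes serious or becomes fatal on study drug is left out of the tables and rates built on TEAEs whenever it keeps its original onset date. Whether that happens in practice depends on a recording rule outside the supplied documents.

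The count cannot be estimated and may be near zero; no document gives a pre-dose event rate, and none supports a figure for serious or fatal cases. The case for acting rests on the cheapness of the change and the importance of the safety tables, not on volume. It is a worthwhile clarification to make before data lock, with medium confidence.

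**What to change.** Extend the definition in SAP 6.6.1 with wording such as: a TEAE is also an adverse event with onset before first dose that increases in severity, becomes serious or becomes fatal within the treatment-emergent window, dated at the worsening. State that the same rule applies to serious and fatal TEAEs and to the incidence rates, in every arm, including shared placebo participants in the full safety set.

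Where the database holds one severity per event, count a worsening as a new record dated at the worsening. If the Master Protocol already requires this, cite the rule in 6.6.1 so that each worsening is counted once.

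Reconcile the start of adverse event recording between the protocol schedule (consent, with review from Master Protocol Screening) and SAP 2.9 footnote 14 (regimen consent form). The SAP's own table also marks review at Master Protocol Screening.

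The cost is a few sentences and some programming on severity, seriousness and outcome data, with record entry at sites if severity is held once per event. The downside is a slightly higher TEAE count in all arms.

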6.6.2 Safety Labs

Summaries and analyses of clinical safety labs are the same as specified in the M-SAP with the revision that abnormal levels will be classified to a toxicity grade based on quantitative grading using National Cancer Institute (NCI) Common Terminology Criteria for Adverse Events (CTCAE) version 5.0 and with the addition that maximum toxicity over all post-baseline visits will be included in shift tables along with visit-specific shifts.

The proportion of participants with ALT >3x ULN, AST >3x ULN, creatinine >1.5x level at the Baseline Visit, and platelet count <75,000/mm³, or with any of the four will be presented as shift tables vs. the status of each participant at baseline for each visit by treatment group in all safety samples. The absolute level and the absolute change from baseline for ALT, AST, creatinine, and platelet count will be summarized as means, standard deviations, medians, and ranges at each visit by treatment group in all safety samples.

6.6.3 ECG Results

Summaries of ECG parameters and findings are the same as specified in the M-SAP.

6.6.4 Vital Signs and Weight

Summaries and analyses of vital signs and weight are the same as specified in the M-SAP.

6.6.5 Suicidality

Summaries of suicidality are the same as specified in the M-SAP.

6.7 Other Analyses

6.7.1 Participant Disposition

All participants consented to the Master Protocol between the time of the first and last consent of a participant assigned to a regimen included in the FAS analysis set will be summarized as a single set for the following events: consented to the Master Protocol, failed screening for the Master Protocol, other reasons not assigned to a regimen (including timing out of the screening window, death, withdrawal of consent, early termination, and administrative termination), and assigned to a regimen. Reasons for Master Protocol screen failure will be summarized.

All participants in the above sample assigned to a regimen will be summarized as two sets (final screening for RGC vs. final screening for a non-RGC regimen) for the following events: consented to a regimen, failed screening for a regimen, other reasons not randomized within a regimen (including timing out of the screening window, death, withdrawal of consent, early termination, and administrative termination), and randomized within a regimen. If a given individual is screened multiple times prior to randomization within a regimen, then the final screening experience of that individual will be summarized. Reasons for RGC screen failure will be summarized separately for all participants screened for RGC whether that was their final screening experience or not.

All participants in the FAS analysis set will be summarized as two sets (randomization to active study drug vs. randomization to placebo) for the following events: initiated regimen-specific study drug, prematurely terminated study participation due to death, withdrawal of consent, early termination, loss to follow-up, or administrative termination, completed 24-week follow up, and completed a safety follow-up visit vs. continued into the OLE. Reasons for withdrawal of consent or early termination after randomization will be summarized.

Any randomized participants excluded from the FAS and EPP analysis sets or included in the FAS analysis set but not contributing to the primary analysis will be identified in a listing together with the reason for their exclusion.

6.7.2 Study Drug Compliance and Tolerance

Summaries of study drug compliance and tolerance are the same as specified in the M-SAP with the clarification that summaries will be reported for the ERO and SRO analysis sets and that date of permanent discontinuation of study drug is the date of last use of double-blind study drug among all participants in a given analysis set.

The number of days of exposure to study drug will be calculated in three ways:

- as the number of days from dose initiation to the final safety assessment during the placebo-controlled period, inclusive,
- as the number of days from dose initiation to drug withdrawal, inclusive, less any interval during which use of study drug was interrupted (individual missed doses will not be subtracted unless noted in the dosage management log), and
- as the number of days from dose initiation to the earlier of final contact during the placebo-controlled period or 28 days after last dose of study drug, inclusive.

The proportion of participants who interrupted study drug or reduced study drug dosage and the time to first study drug interruption or dosage reduction will be summarized. The number of days of exposure to a reduced dosage of study drug will be summarized.

6.7.3 Concomitant Medication Use

Summaries of concomitant medication use are the same as specified in the M-SAP with the clarification that medications taken at baseline and those initiated after first dose of study drug will be separately summarized and will be classified by ATC Therapeutic class and WHODrug Preferred base name.

6.7.4 Medical History

Medical histories will be summarized by MedDRA system organ class, high level term, and preferred term in the STF and SRO analysis sets.

6.7.5 Blindedness

The proportions of participants and site investigators who report on the Exit Questionnaire a guess of active vs. placebo treatment assignment, each level of surety of that guess, and each of five pre-specified reasons for making a treatment assignment will be summarized by treatment group in the FAS and ERO analysis sets. Treatment-dependent differences in the proportion guessing active treatment assignment will be tested among all respondents and among those stating they are at least somewhat sure of their guess by Fisher's exact test and the difference in proportion guessing active treatment assignment will be estimated with confidence bounds.

6.7.6 Protocol Deviations

The number of major and minor protocol deviations will be summarized by type of deviation and treatment group in all analysis sets. Listings of all protocol deviations will be produced.

6.7.7 Impact of COVID-19 Pandemic

The proportions of planned assessments missed due to COVID-19 restrictions or disruptions will be summarized by treatment group, visit, and type of assessment in the FAS and ERO analysis sets. Protocol deviations that resulted from COVID-19 restrictions or disruptions will be summarized by treatment group and type of deviation in the FAS and ERO analysis sets and listed.

7. Validation

7.1 Primary Efficacy Analysis

Validation of the primary efficacy analysis is the same as specified in the M-SAP.

